**List of Abbreviations**

Abbreviation	Definition
AE	Adverse event
CAS	Cranial Autonomic Symptoms
CRF	Case report forms
ITT	Intent-to-treat
MH	Medical history
min	Minimum
max	Maximum
MedDRA	Medical dictionary for regulatory activities
NCI CTCAE	Common Terminology Criteria for Adverse Events published by the National Cancer Institute
NE	Not evaluable
PACAP38	Pituitary adenylate cyclase activating polypeptide-38
PK	Pharmacokinetics
SAE	Serious adverse event
SOC	System organ class
STD	Standard deviation
WHO	World health organization

## **2. Revision History**

Statistical Analysis Plan (SAP) Version 1 was approved prior to the first visit when a patient receives study drug or any other protocol intervention.

### 3. Study Objectives

Table 3.1 provides the objectives and endpoints of the study.

**Table 3.1. Objectives and Endpoints**

Objectives	Endpoints
Primary Objective	
To test the hypothesis that a single IV dose of LY3451838 is superior to placebo in the prevention of migraine in treatment-resistant migraine patients	The mean change from baseline in the number of monthly migraine headache days during the 1-month treatment phase (episodic and chronic migraine) a
Secondary Objectives	
To compare LY3451838 with placebo with respect to prevention of monthly headache days	The mean change from baseline in the number of monthly headache days during the 1-month treatment phase
To compare LY3451838 with placebo with respect to 50% response rate	The percentage of patients with $\geq 50\%$ reduction from baseline in monthly migraine headache days during the 1-month treatment phase
To evaluate the safety and tolerability of a single dose of LY3451838 in treatment-resistant migraine patients	TEAEs SAEs
To characterize the pharmacokinetics of LY3451838 following a single IV dose in treatment-resistant migraine patients	LY3451838 Cmax and AUC

The image consists of a large, bold, red text "CCI" centered on a solid black rectangular background. The font is a sans-serif style.

a Episodic migraine is defined as 4 to 14 migraine headache days and <15 headache days per 1-month period in the prospective baseline period. Chronic migraine is defined as at least 15 headache days per 1-month period in the prospective baseline period, of which at least 8 are migraine.

The image consists of a large, bold, red text "CCI" centered on a solid black rectangular background. The font is a sans-serif style.

## 4. Study Design

### 4.1. Summary of Study Design

Study LAJB is a multicenter, randomized, double-blind, parallel, placebo-controlled study of LY3451838 in patients who meet the International Classification of Headache Disorders version 3 (ICHD-3) criteria for a diagnosis of migraine with or without aura, or chronic migraine, and who have previously failed 2 to 4 categories of standard-of-care treatments for migraine prevention. The study has 4 periods, including the screening period, baseline for J1H-MC-LAJB(a) Clinical Protocol Page 9 LY3451838 eligibility, double-blind treatment phase, and follow-up assessment of headache episodes and related information.

### 4.2. Determination of Sample Size

The study will screen an estimated 110 potential patients to ensure randomization of approximately 60 migraine patients. Enrollment will be stratified by type of migraine, episodic versus chronic, and patients will be randomly assigned to either LY3451838 or placebo in a 1:1 allocation ratio within each stratum. CCI [REDACTED]

The analysis will be conducted using all randomized patients, and it is assumed that approximately 2% of the patient population will dropout during the 28 days treatment period.

CCI

Enrolling approximately 60 patients who are stratified by type of migraine, episodic versus chronic, and randomly assigned to either LY3451838 or placebo in a 1:1 allocation ratio within each stratum will provide approximately CCI [REDACTED]

CCI

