10.1. Sample Size Determination

The study will screen an estimated 110 potential patients to ensure randomization of approximately 60 migraine patients. Enrollment will be stratified by type of migraine, episodic versus chronic, and patients will be randomly assigned to either LY3451838 or placebo in a 1:1 allocation ratio within each stratum. Enrollment in the chronic migraine stratum will be capped so that no more than approximately 50% of the randomized population will be patients with chronic migraine.

The analysis will be conducted using all randomized patients, and it is assumed that approximately 2% of the patient population will dropout during the 28 days treatment period.

The study will be considered successful if there is at least a [REDACTED] CCI probability that the number of monthly migraine headache days with LY3451838 treatment is [REDACTED] CCI days less than the number of monthly migraine headache days with placebo treatment [REDACTED]

Enrolling approximately 60 patients who are stratified by type of migraine, episodic versus chronic, and randomly assigned to either LY3451838 or placebo in a 1:1 allocation ratio within each stratum will provide approximately [REDACTED] CCI

CCI

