10.3.3. Efficacy Analyses

10.3.3.1. Primary Analyses

The primary analysis will be performed using an analysis of covariance (ANCOVA) model for the change from baseline in the monthly number of migraine headache days. The model will include randomized treatment and type of migraine as fixed effects and the baseline number of monthly migraine headache days as a covariate. The analysis will use a non-informative prior for the treatment effect. The treatment group means, treatment contrast, and their respective 95% credible regions as well as the success criterion will be based on the posterior treatment effect distributions.

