## 5. A Priori Statistical Methods

### 5.1. General Considerations

Efficacy analyses will be conducted on the full analysis set (FAS). Safety analyses will be conducted on the safety analysis set (SAF) which are described in Section 5.2. When mean change from baseline is assessed, the patient will be included in the analysis only if the patient has a baseline and a postbaseline measurement.

In general, for analyses of numeric outcome measures during the treatment phase, baseline value is defined as the last observation at or before Visit 3. Treatment effects will be evaluated based on a 2-sided significance level of 0.05.

A Bayesian analysis will be performed for the primary efficacy endpoint, and the corresponding frequentist analyses will be conducted as a supplemental analysis. All other statistical inference will be performed using frequentist methods.

For continuous variables, descriptive statistics will include the number of patients, mean, median, standard deviation, minimum, and maximum. Categorical variables will be summarized using the number and percentage of patients.

SAS® software version 9.4 or higher will be used to perform statistical analyses, unless otherwise specified.

The following terms and data handling conventions defined in [Table 5.1](#) will be used in the analysis.

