## 5.11. Efficacy Analyses

### 5.11.1. Primary Endpoint and Primary Methodology

The primary analysis will be performed using a linear model for the change from baseline in the monthly number of migraine headache days within the Bayesian framework. The model will include randomized treatment and type of migraine as fixed effects and the baseline number of monthly migraine headache days as a covariate. The analysis will use a non-informative prior for the treatment effect. CCI

The logo consists of the letters 'CCI' in a large, bold, red sans-serif font. The letters are slightly overlapping, with 'C' on the left, 'C' in the middle, and 'I' on the right. The background is a solid black rectangle.

Additionally, if the compliance rate for a monthly interval is  $\leq 50\%$ , then the number of migraine headache days derived from the ePRO diary data for that 1-month period will be considered missing.

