### **5.11.2. Sensitivity Analyses for Primary Endpoint**

All patients have over 50% diary entry compliance in the 1-month treatment phase and no subject has monthly migraine headache days set to missing. Therefore, the sensitivity analysis will not be performed.

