#### **5.11.4. Secondary and Exploratory Efficacy Endpoints**

Due to insufficient enrollment only the primary endpoint is to be evaluated. The data for all secondary and exploratory endpoints is available in the SDTMs for any analyses to be performed if needed.

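### Does the 60-patient sample-size statement in SAP 4.2 need recalculating because SAP 5.11.4 reports insufficient enrollment?

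*SAP*

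**What the plan says.** SAP 4.2 (Determination of Sample Size) is written in the future tense. About 110 patients are to be screened "to ensure randomization of approximately 60 migraine patients", and a second sentence, beginning "Enrolling approximately 60 patients who are stratified by type of migraine", attaches an approximate value to that size. The value is redacted. Protocol 10.1 has the same structure and shows what the value refers to, since it opens the criterion with "The study will be considered successful if there is at least a" and then redacts the threshold.

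Two later SAP sections were plainly written with knowledge of how the trial had gone. SAP 5.11.4 states "Due to insufficient enrollment only the primary endpoint is to be evaluated". SAP 5.11.2 reports "All patients have over 50% diary entry compliance in the 1-month treatment phase". Neither gives a count.

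For the primary analysis, SAP 5.11.1 says "The analysis will use a non-informative prior for the treatment effect". Protocol 10.3.3.1 adds that the group means, the contrast, "their respective 95% credible regions as well as the success criterion will be based on the posterior treatment effect distributions". SAP 5.1 adds that "the corresponding frequentist analyses will be conducted as a supplemental analysis".

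**The concern.** A single document says both that 60 patients will be randomised and that too few were enrolled. The authors had treatment-phase diary data, so they could have stated the achieved number, yet the only operating characteristic offered is conditional on 60.

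This matters more than usual for two reasons. First, only the primary endpoint is kept, so the success call carries the whole efficacy conclusion. Second, the rule fixes a posterior probability against a margin. With a flat prior, such a rule does not hold its false-positive rate constant as a significance test does. As the sample shrinks, success becomes less likely if the drug works as planned and more likely if it does nothing. A reader who carries the 60-patient figure over to a smaller trial would give a success call too much weight.

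**Working it through.** **Inputs.** The current values are redacted, so these come from the marked-up text of section 10.1 in Protocol Appendix 7 and are assumptions here:

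- success if the posterior probability that the difference is below −1.5 days is at least 0.60;
- effects of 2.57 days (episodic) and 3.70 days (chronic), mean (2.57 + 3.70)/2 = 3.135;
- standard deviations (SDs) of change 2.50 and 3.75, separated from old and new digits that run together in the extracted text; the other reading is 3 and 5.27;
- 2% dropout, 1:1 allocation, half the patients chronic.

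The extracted text also carries strike-through marks around the sentences that hold the SDs, so their standing in the current text cannot be confirmed.

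**Formulas.** With N randomised:

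- n = 0.98N
- SE = √[((SD_E² + SD_C²)/2) × 4/n]
- required observed reduction c = 1.5 + t(0.60, n−4) × SE
- P(success, planned effect) = Φ((3.135 − c)/SE)
- P(success, zero effect) = Φ(−c/SE)

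**The plan's own figure first.** At N = 60, n = 58.8 and the mean variance is (6.25 + 14.0625)/2 = 10.156. SE = √(10.156 × 4/58.8) = 0.831 and c = 1.5 + 0.2546 × 0.831 = 1.712. P(success, planned) = Φ((3.135 − 1.712)/0.831) = 95.7%. The amendment summary gives about 94%. A simulation of the full ANCOVA gave 95.6%. The figure reproduces to within two percentage points.

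The reading of the SDs is supported in two ways. The pair 3 and 5.27 gives only 88.6% at N = 60 with the new effects. The same pair gives 79.4% for the superseded 120-patient design with a 2.35-day effect, close to the 77% stated for it.

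**What a smaller trial would do.** The achieved N is not in the visible documents, so a range is shown.

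| N | SE (2.50/3.75) | c | Success: planned / zero effect | Same with SDs 3/5.27 |
|---|---|---|---|---|
| 60 | 0.831 | 1.712 | 95.7% / 2.0% | 88.6% / 5.5% |
| 50 | 0.911 | 1.732 | 93.8% / 2.9% | 86.0% / 7.0% |
| 40 | 1.018 | 1.760 | 91.2% / 4.2% | 82.6% / 8.8% |
| 30 | 1.176 | 1.801 | 87.2% / 6.3% | 78.2% / 11.4% |
| 20 | 1.440 | 1.871 | 81.0% / 9.7% | 72.1% / 15.1% |

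The direction feared is confirmed. The required observed reduction does become stricter, from 1.71 days at N = 60 to 1.87 at N = 20, but not fast enough to keep the zero-effect rate level. At about 50 patients the change is small.

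**What the plan delivers at the achieved N without any edit.**

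- *Numbers by arm.* SAP 5.2 puts all randomised patients in the full analysis set. SAP 5.5 summarises disposition on that set, SAP 5.7 summarises baseline data by treatment group, and SAP 5.1 includes the number of patients among the descriptive statistics.
- *Precision.* The 95% credible region in Protocol 10.3.3.1 widens as N falls. Its half-width, approximated as 1.96 × SE with SDs 2.50/3.75, is 1.6 days at N = 60 and 2.8 days at N = 20.
- *A result whose error rate does not drift.* The supplemental frequentist analysis in SAP 5.1 is judged at a two-sided 0.05 level, whatever the sample size.

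**The case for a change.** The best case for a change is that the sponsor thought the shortfall serious enough to set aside every secondary and exploratory efficacy endpoint, yet did not say what it does to the endpoint it kept. The rise in zero-effect success is easily missed by readers used to significance tests, and a paragraph would cost almost nothing.

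Much of this stands. The visible text does lack the achieved N, the two sections do sit awkwardly together, and the behaviour of the rule is as described. It would help a reader to have 60 labelled as the original plan and to see the number randomised by arm and migraine type. If success probabilities at the achieved size were given as well, they should use the planning inputs under both the planned and the zero effect.

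It does not amount to a fault in the plan. A sample-size section records the basis on which the size was chosen, and this one agrees with Protocol 10.1. A restated value could lie under the redactions in SAP 4.2 or 5.11.1, so its absence cannot be established. The shortfall is not quantified, so any argument that rests on 20 to 40 patients rests on a guess. The results also depend on which SDs apply: the zero-effect rate at N = 60 is 2.0% with one pair and 5.5% with the other, a gap about as large as that between N = 60 and N = 30 with the first pair. Finally, once the data exist, the interval tells the reader more than a recalculated planning probability.

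How the statements about observed data in SAP 5.11.2 and 5.11.4 fit a revision history that names only Version 1, approved before first dosing, is a separate question from the sample-size paragraph.

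**Conclusion.** No change to the plan is needed. SAP 4.2 is a conditional planning statement, not a miscalculation, and its figure reproduces (95.7% against about 94%). What is missing from the visible text is a reporting detail: the achieved number, and a label saying that 60 was the original intention.

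The effect of a shortfall cannot be sized from these documents. It is small if about 50 or more patients were randomised. At 20 it would be about 81% and 10% (planned and zero effect) with SDs 2.50/3.75, or 72% and 15% with SDs 3/5.27. These figures assume the margin, threshold and effects from the amendment summary, equal strata and 2% dropout. Restating them would leave the estimate, model, analysis set and success rule as they are. The counts by arm, the credible region and the supplemental frequentist result already give a reader what is needed to judge a success call at the size achieved.

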### 4.3. Method of Assignment to Treatment

Following a 1-month prospective baseline period, eligible patients will be stratified by type of migraine (episodic or chronic) and then randomly assigned in a 1:1 ratio within each stratum to receive LY3451838 or placebo. Treatment assignment will be determined by a computer-generated randomization sequence using an interactive web response system (IWRS).

CCI

## 5. A Priori Statistical Methods

### 5.1. General Considerations

Efficacy analyses will be conducted on the full analysis set (FAS). Safety analyses will be conducted on the safety analysis set (SAF) which are described in Section 5.2. When mean change from baseline is assessed, the patient will be included in the analysis only if the patient has a baseline and a postbaseline measurement.

In general, for analyses of numeric outcome measures during the treatment phase, baseline value is defined as the last observation at or before Visit 3. Treatment effects will be evaluated based on a 2-sided significance level of 0.05.

A Bayesian analysis will be performed for the primary efficacy endpoint, and the corresponding frequentist analyses will be conducted as a supplemental analysis. All other statistical inference will be performed using frequentist methods.

For continuous variables, descriptive statistics will include the number of patients, mean, median, standard deviation, minimum, and maximum. Categorical variables will be summarized using the number and percentage of patients.

SAS® software version 9.4 or higher will be used to perform statistical analyses, unless otherwise specified.

The following terms and data handling conventions defined in [Table 5.1](#) will be used in the analysis.

**Table 5.1. Date and Timing Conventions**

Term	Definitions or Rule
Study Day	If assessment is on or after date of first treatment dose then (date of assessment) – (date of first study treatment dose) + 1 If assessment precedes first treatment dose then (date of assessment) – (date of first study treatment dose)
Baseline value	Baseline value is defined as the last reported assessment on or before the first dose (or discontinuation, if no treatment is given).
Screening period	Date of informed consent (Visit 1) through the day prior to Visit 2; includes all dates of study participation for those without Visit 2.
Baseline period	Visit 2 date through the day prior to study drug administration (for those receiving study drug); Visit 2 date through end of study participation for those who participating in Visit 2 but not receiving study drug.
Study treatment period	The 1-month double-blind treatment phase begins on the date of study drug administration (Visit 3) and continues through date of Month 1 visit (Visit 5) for those participating in Visit 5; continues through study withdrawal for those withdrawing prior to Visit 6 (Month 1.5). If patients do not attend Visit 5 but continue on study, the end of study treatment period will be the expected date of Visit 5 (i.e.30 days after Visit 3).

Follow-up period	Patients who continue on study after Visit 5 (or beyond expected date of Visit 5, if patient does not attend Visit 5 but attends later visits) will enter the follow-up period the day after the Visit 5 date (or expected date, where relevant), and continue for up to 140 days post-dose.
------------------	--

## 5.2. Analysis Sets

The following analysis sets used for analysis are defined in [Table 5.2](#) below.

**Table 5.2. List of Analysis Sets**

Analysis Set	Definitions or Rule
Enrolled Patients	Includes all patients who have signed the informed consent
Screen Failures	Includes all patients who have signed the informed consent but are not treated or randomized
Full Analysis Set (FAS)	The FAS will include all patients who have been randomized to study treatment following the intent to treat (ITT) principle. Patients in this set will be grouped according to their allocated treatment. All patient characteristic and efficacy data will be presented using the FAS.
Per-protocol Set (PPS)	The PPS will include all patients who have been randomized to study treatment and did not have any major protocol deviations. Patients in this set will be grouped according to their allocated treatment. Additional efficacy analyses may be conducted on PPS.
Safety Analysis Set (SAF)	The SAF will include all patients who have been randomized to study treatment and have received at least 1 dose of study treatment (LY3451838 or placebo). Patients will be grouped according to actual treatment received.

## 5.3. Handling of Dropouts or Missing Data

Missing data imputation for adverse event medical history, and concomitant medication dates will be performed as follows. Imputed dates will be used to determine treatment-emergent or concomitant status, but imputed portions of dates (or times) will not be displayed in listings.

Start dates/Dates of onset:

- Completely missing: impute as patient's treatment date
- Year present, month and day missing:
  - o If year is the same as year of treatment date, impute as treatment date
  - o Otherwise, impute as December 31st
- Month and year present, day missing:
  - o If month and year are the same as treatment date, impute as treatment date
  - o Otherwise, impute as last day of the month
- Time missing:
  - o If same date as treatment date, impute as start time of treatment
  - o Otherwise impute as 23:59

End dates / resolution dates:

- Completely missing: impute as date of study completion or withdrawal from study
- Year present, month and day missing: Impute as December 31st
- Month and year present, day missing: Impute as the last day of the month
- Time missing: Impute as 23:59

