9.2. Adverse Events

A clinical trial AE is any untoward medical event associated with the use of a drug or drug delivery system in humans, whether or not it is considered related to that drug or drug delivery system.

Investigators are responsible for monitoring the safety of patients who have entered this study and for alerting Lilly or its designee to any event that seems unusual, even if this event may be considered an unanticipated benefit to the patient.

The investigator is responsible for the appropriate medical care of patients during the study.

Investigators must document their review of each laboratory safety report and ECG.

The investigator remains responsible for following, through an appropriate health care option, AEs that are serious or otherwise medically important, considered related to the investigational

product or the study, or that caused the patient to discontinue the investigational product before completing the study. The patient should be followed until the event resolves, stabilizes with appropriate diagnostic evaluation, or is reasonably explained. The frequency of follow-up evaluations of the AE is left to the discretion of the investigator.

Lack of drug effect is not an AE in clinical studies, because the purpose of the clinical study is to establish treatment effect. However, any worsening of the primary study condition should be recorded as an AE.

After the ICF is signed, study site personnel will record via EDC the occurrence and nature of each patient's pre-existing conditions, including clinically significant signs and symptoms of the disease under treatment in the study. In addition, site personnel will record via eCRF any change in the condition(s) and any new conditions as AEs. Investigators should record their assessment of the potential relatedness of each AE to protocol procedure or investigational product via EDC.

The investigator will interpret and document whether or not an AE has a reasonable possibility of being related to study treatment, study device, or a study procedure, taking into account the disease, concomitant treatment, and pathologies.

A "reasonable possibility" means that there potentially is a cause and effect relationship between the investigational product, study device, and/or study procedure and the AE.

The investigator will use AE follow-up forms to record additional details regarding AEs related to injection sites and hypersensitivity events.

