### **5.12. Safety Analyses**

#### **5.12.1. Adverse Events**

TEAEs are defined as the reported AEs that first occurred or worsened during the postbaseline phase compared with baseline phase. For each TEAE, the severity level of the event (mild, moderate, or severe) will be determined by patient or physician opinion. The MedDRA Lowest Level Term (LLT) will be used in the treatment-emergent computation. For each LLT, the maximum severity at baseline will be used as the baseline severity. If the maximum severity during postbaseline is greater than the maximum baseline severity, the event is considered as treatment-emergent for the specific postbaseline period.

For each patient and TEAE, the maximum severity for the MedDRA level being displayed (PT, High Level Term, or SOC) is the maximum postbaseline severity observed from all associated LLTs mapping to that MedDRA level.

For events that are sex-specific, the denominator and computation of the percentage will include only patients from the specific sex.

The safety and tolerability of treatment will be assessed by summarizing (using standard descriptive statistics) and listed on the SAF. The following parameters will be reported:

- TEAEs
- SAEs
- AEs leading to discontinuation
- Potential hypersensitivity events
- AEs related to injection site reactions
- Vital signs
- Physical and neurological examinations
- ECGs
- Laboratory measurements
- CBB

Additional analysis will be performed as required.

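### Three start-date rules in SAP 5.3 impute the treatment date without checking the end date, so an AE known to have ended before dosing could be counted as a TEAE

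*SAP*

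**What the plan says.** SAP 5.3 gives one set of date rules for adverse events, medical history and concomitant medication. Three start-date rules lead to the treatment date:

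- Nothing known: "Completely missing: impute as patient's treatment date".
- Year only: "If year is the same as year of treatment date, impute as treatment date".
- Month and year only: "If month and year are the same as treatment date, impute as treatment date".

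Other partial starts go to 31 December of the known year or, for a known month, follow this rule: "Otherwise, impute as last day of the month". End dates have their own list of rules. Nothing requires the imputed start to precede the end.

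The section also says what the result is used for: "Imputed dates will be used to determine treatment-emergent or concomitant status". SAP 5.12.1 then defines the events of interest: "TEAEs are defined as the reported AEs that first occurred or worsened during the postbaseline phase compared with baseline phase". It applies this by comparing severities within each MedDRA Lowest Level Term: "If the maximum severity during postbaseline is greater than the maximum baseline severity, the event is considered as treatment-emergent". No clause removes an event whose recorded end precedes dosing.

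**The concern.** Treating an event as treatment-emergent when its timing is unknown is a sensible default. Here the timing may not be unknown. A recorded end before dosing proves that the event was over before the drug was given, yet the rule as written gives it an on-treatment start. The record then contradicts itself, because it starts after it ends, and it could carry a treatment-emergent flag.

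Such events can arise. Protocol Section 9.2 starts recording at consent: "After the ICF is signed, study site personnel will record via EDC the occurrence and nature of each patient's pre-existing conditions". Later changes and new conditions are recorded as AEs. The Schedule of Activities then puts at least a month between consent and dosing.

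TEAEs are a secondary endpoint (SAP Table 3.1) and stay on the list to be reported in SAP 5.12.1. They also feed the registry table of non-serious events in SAP 5.18.

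**Working it through.** The documents give no figure that depends on this rule, so there is nothing to reproduce. The check applies the written rules to example records and then to a systematic enumeration.

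**Time available for pre-dose events** (Protocol Table LAJB 2.1 and its footnote a). Minimum: 3 days of screening + 30 days of baseline = 33 days. Maximum: 90 + 40 + 5 scheduling days = 135 days.

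**Example records.** Assumed treatment date: 20 June 2021. A record is flagged if its imputed start is on or after that date.

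| Start as recorded | Known end | Imputed start | After its own end? | Flagged? |
|---|---|---|---|---|
| June 2021, day missing | 10 June 2021 | 20 June 2021 | yes | yes |
| 2021 only | 10 May 2021 | 20 June 2021 | yes | yes |
| wholly missing | 10 May 2021 | 20 June 2021 | yes | yes |
| May 2021, day missing | 10 May 2021 | 31 May 2021 | yes | no |
| 2020 only | 10 June 2020 | 31 December 2020 | yes | no |

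The first three rows are the problem. The last two are inconsistent records, but they stay before dosing and do no harm to the TEAE count.

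**Does the severity comparison in SAP 5.12.1 catch it?** Only sometimes. Once the event is moved to the postbaseline phase, its own severity no longer counts towards the baseline maximum. The flag is suppressed only if a separate baseline record of the same term has equal or greater severity.

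**Enumeration.** Assumptions: every dosing date in one calendar year, onset 1 to W days before dosing, duration 0 to 13 days, only events that ended before dosing, all combinations weighted equally. W is 33 (the minimum), 60 (an intermediate value) and 135 (the maximum). Share given an on-treatment start:

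| What is missing from the start | W = 33 | W = 60 | W = 135 |
|---|---|---|---|
| day | 35.1% | 17.4% | 7.2% |
| day and month | 94.5% | 90.8% | 80.5% |
| whole date | 100% | 100% | 100% |

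With one added condition, start = the earlier of the imputed start and the known end, every cell becomes 0%.

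These shares are conditional. They apply to pre-dose events that have a known end and that particular kind of incomplete start. They do not estimate how many such records the trial has.

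**Scale.** About 60 patients randomized 1:1 gives about 30 per arm. One misflagged patient adds 1/30 = 3.3 percentage points to a rate in that arm. SAP 5.18 allows non-serious terms below 5% in every arm to be left out of the registry table. Going from one patient to two, 1/30 = 3.3% to 2/30 = 6.7%, would cross that line.

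**The case against.** The case on the other side has five parts.

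1. **The rule is cautious.** It over-counts TEAEs and ignores treatment arm, so by design it favours neither. This stands, and it limits the harm. But caution is an argument for cases where timing is unknown, not for overriding a recorded end date.

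2. **The definition already excludes such events.** An event that resolved before dosing did not first occur or worsen after baseline, and the protocol's glossary definition of a TEAE points the same way. That is the intent, but SAP 5.3 says that imputed dates decide the status, and a program written to the SAP would follow that explicit rule.

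3. **The error would be noticed.** Protocol Appendix 3.2 plans standard computer edits, and listings show the dates as reported. A careful reader might spot a pre-dose end beside a TEAE flag. General data edits do not correct a derivation rule, however, and the listing would not show the imputed start that explains the flag.

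4. **Most partial dates are safe.** This is correct. A reader might infer that every missing or partial start goes to the treatment date. It does not: a start in a known earlier month or year stays before dosing.

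5. **Past preventives.** Every patient has 2 to 4 earlier preventive failures, so a reader might infer that old preventives will commonly look concomitant. The documents do not support that. Inclusion Criterion 6 says only that the failures fall within the past 10 years and says nothing about how well their dates are known. A start in a known earlier year is imputed within that year. The SAP also does not say that start date alone decides concomitant status, and for pre-existing conditions SAP 5.7 classifies by end date. What remains is narrow: a medication with a wholly missing start, or one known only to the treatment year or treatment month, and a known pre-dose end would get an impossible start date.

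**Conclusion.** The point holds within limits. Under SAP 5.3 as written, an AE with a known end before dosing could be given a start after its own end and be counted as a TEAE, if its start is wholly missing, known only to the treatment year, or known only to the treatment month. This is a wrong result from a stated rule, not merely a missing detail.

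It is a minor matter. It needs two things together, an incomplete start and a known pre-dose end. The documents give no frequency for that, and it is probably low. The primary analysis is untouched, and nothing suggests that a conclusion would change.

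The 3.3 points per misflagged patient rests on the planned 30 per arm. SAP 5.11.4 reports insufficient enrollment, so the arms actually analysed may be smaller and one patient would then weigh more: at an assumed 20 per arm, 1/20 = 5 points. Smaller arms would also hold fewer records.

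**What to change.** Add to SAP 5.3: an imputed start date may not be later than a known end date; and a record whose end date, full or partial taken at its latest possible value, precedes dosing is not treatment-emergent. Apply the same cap to medication dates.

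The SAP's own end-date rules already supply the latest value for a partial end (31 December, or the last day of the month), so the program can compare against those. With dosing on 20 June, an end in May with the day missing becomes 31 May and the event is not treatment-emergent. An end in June with the day missing becomes 30 June and the cautious default stays. For a dosed patient, a wholly missing end is imputed as study completion or withdrawal, so the cap does not act.

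The missing-time rule has the same gap for an event that ended on the dosing day before the infusion. The same condition can cover it where an end time is recorded.

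The cost is one sentence and one programming condition. No design feature changes, and the default remains where timing is truly unknown.
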